### **Registration of Clinical Studies and Disclosure of Results**

The sponsor will register and disclose the existence of and the results of clinical studies as required by law. The disclosure of the final study results will be performed after the end-of-study in order to ensure the statistical analyses are relevant.

#### **10.3.8. Data Quality Assurance**

##### **Data Quality Assurance/Quality Control**

Steps to be taken to ensure the accuracy and reliability of data include the selection of qualified investigators and appropriate study sites, review of protocol procedures with the investigator and study-site personnel before the study, and periodic monitoring visits by the sponsor. Written instructions will be provided for collection, handling, storage, and shipment of samples.

Guidelines for eCRF completion will be provided and reviewed with study-site personnel before the start of the study.

The sponsor will review the eCRF for accuracy and completeness after transmission to the sponsor; any discrepancies will be resolved with the investigator or designee, as appropriate. After upload of the data into the study database they will be verified for accuracy and consistency with the data sources.

### 10.3.9. Case Report Form Completion

Case report forms are prepared and provided by the sponsor for each participant in electronic format. All data relating to the study will be recorded in the eCRF or eCOA. All eCRF entries, corrections, and alterations must be made by the investigator or authorized study-site personnel. The investigator must verify that all data entries in the eCRF are accurate and correct.

The study data will be transcribed by study-site personnel from the source documents onto an eCRF, if applicable. Study-specific data will be transmitted in a secure manner to the sponsor.

Worksheets may be used for the capture of some data to facilitate completion of the eCRF. Any such worksheets will become part of the participant's source documents. Data must be entered into the eCRF in English. The eCRF must be completed as soon as possible after a participant visit and the forms should be available for review at the next scheduled monitoring visit.

If necessary, queries will be generated in the electronic data capture (eDC) tool. If corrections to an eCRF are needed after the initial entry into the eCRF, this can be done in either of the following ways:

- Investigator and study-site personnel can make corrections in the eDC tool at their own initiative or as a response to an auto query (generated by the eDC tool).
- Sponsor or sponsor delegate can generate a query for resolution by the investigator and study-site personnel.

### 10.3.10. Source Documents

At a minimum, source documents consistent in the type and level of detail with that commonly recorded at the study site as a basis for standard medical care must be available for the following: participant identification, eligibility (including relevant medical history, including anything related to footnotes [h](#) and [i](#) to the [Schedules of Activities](#) in Section 1.3.3), and study identification; study discussion and date of signed informed consent; dates of visits; results of safety and efficacy parameters as required by the protocol; record of all AEs and follow-up of AEs; concomitant therapy; study vaccine receipt/dispensing/return records; study vaccine administration information; and date of study completion and reason withdrawal from the study, if applicable.

The author of an entry in the source documents should be identifiable. Given that PROs are reports of a patient's health condition that come directly from the patient, without interpretation by a clinician or anyone else, the responses to ePRO measures entered by study participants into source records cannot be overridden by site staff or investigators.

Up to protocol amendment 7, participant- and investigator-completed scales and assessments designated by the sponsor (ie, SIC) will be recorded directly into an eDevice and will be considered source data. The participant's e-Diary used to collect information regarding solicited signs and symptoms after vaccination will be considered source data. The documentation of the positive RT-PCR result that serves as a trigger to start procedures for COVID-19 follow-up, will be considered source data.

Specific details required as source data for the study and source data collection methods will be reviewed with the investigator before the study and will be described in the monitoring guidelines (or other equivalent document).

An eSource system may be utilized, which contains data traditionally maintained in a hospital or clinic record to document medical care (eg, electronic source documents) as well as the clinical study-specific data fields as determined by the protocol. This data is electronically extracted for use by the sponsor. If eSource is utilized, references made to the CRF in the protocol include the eSource system but information collected through eSource may not be limited to that found in the eCRF.

### **10.3.11. Monitoring**

The sponsor will use a combination of monitoring techniques (central, remote, or on-site monitoring) to monitor this study.

The sponsor will perform on-site monitoring visits as frequently as necessary, if allowed per local regulations. If on-site monitoring visits are not possible due to local regulations, restrictions and guidance, the monitor will conduct site monitoring visits and activities remotely. Additional on-site monitoring visits may be needed at a later moment in time to catch up on source data review. Remote source data review of electronic records might be performed if possible and if allowed by local/national regulations, restrictions and guidance.

The monitor will record dates of the visits in a study site visit log that will be kept at the study site. The first post-initiation visit will be made as soon as possible after enrollment has begun. At these visits, the monitor will review the source documents (eg, hospital/clinic/physician's office medical records) to ensure adherence to the protocol. The nature and location of all source documents will be identified to ensure that all sources of original data required to complete the eCRF are known to the sponsor and study-site personnel and are accessible for review by the sponsor study-site contact. If electronic records are maintained at the study site, the method of review must be discussed with the study-site personnel.

Direct access to source documents (medical records) must be allowed for the purpose of source document review and may be needed to ensure that the recorded data are consistent with the original source data. Findings from this review will be discussed with the study-site personnel. The sponsor expects that during monitoring visits, the relevant study-site personnel will be available, the source documents will be accessible, and a suitable environment will be provided for review of study-related documents. The monitor will meet with the investigator on a regular basis during the study to provide feedback on the study conduct.

In addition to on-site monitoring visits, remote contacts can occur. It is expected that during these remote contacts, study-site personnel will be available to provide an update on the progress of the study at the site.

Central monitoring will take place for data identified by the sponsor as requiring central review.

### **10.3.12. On-Site Audits**

Representatives of the sponsor's clinical quality assurance department may visit the study site at any time during or after completion of the study to conduct an audit of the study in compliance with regulatory guidelines and company policy. Remote auditing techniques may also be utilized, if necessary. These audits will require access to all study records, including (electronic) source documents as allowed per local regulations, for inspection. Participant privacy must, however, be respected. The investigator and study-site personnel are responsible for being present and available for consultation during routinely scheduled study-site audit visits conducted by the sponsor or its designees.

Similar auditing procedures may also be conducted by agents of any regulatory body, either as part of a national GCP compliance program or to review the results of this study in support of a regulatory submission. The investigator should immediately notify the sponsor if he or she has been contacted by a regulatory agency concerning an upcoming inspection.

### **10.3.13. Record Retention**

In compliance with the ICH/GCP guidelines, the investigator/institution will maintain all eCRF and all source documents that support the data collected from each participant, as well as all study documents as specified in ICH/GCP Section 8, Essential Documents for the Conduct of a Clinical Trial, and all study documents as specified by the applicable regulatory requirement(s). The investigator/institution will take measures to prevent accidental or premature destruction of these documents.

Essential documents must be retained until at least 2 years after the last approval of a marketing application in an ICH region and until there are no pending or contemplated marketing applications in an ICH region or until at least 2 years have elapsed since the formal discontinuation of clinical development of the investigational product. These documents will be retained for a longer period if required by the applicable regulatory requirements or by an agreement with the sponsor. It is the responsibility of the sponsor to inform the investigator/institution as to when these documents no longer need to be retained.

If the responsible investigator retires, relocates, or for other reasons withdraws from the responsibility of keeping the study records, custody must be transferred to a person who will accept the responsibility. The sponsor must be notified in writing of the name and address of the new custodian. Under no circumstance shall the investigator relocate or dispose of any study documents before having obtained written approval from the sponsor.

If it becomes necessary for the sponsor or the appropriate regulatory authority to review any documentation relating to this study, the investigator/institution must permit access to such reports.

### **10.3.14. Study and Site Start and Closure**

#### **First Act of Recruitment**

The first site open is considered the first act of recruitment and it becomes the study start date.

## Study/Site Termination

The sponsor reserves the right to close the study site or terminate the study at any time for any reason at the sole discretion of the sponsor. Study sites will be closed upon study completion. A study site is considered closed when all required documents and study supplies have been collected and a study-site closure visit has been performed.

The investigator may initiate study-site closure at any time, provided there is reasonable cause and sufficient notice is given in advance of the intended termination.

Reasons for the early closure of a study site by the sponsor or investigator may include but are not limited to:

- Failure of the investigator to comply with the protocol, the requirements of the IEC/IRB or local health authorities, the sponsor's procedures, or GCP guidelines
- Inadequate recruitment of participants by the investigator
- Discontinuation of further study vaccine development

## **10.4. Appendix 4: Adverse Events, Serious Adverse Events, Adverse Events of Special Interest, Medically-attended Adverse Events, Product Quality Complaints, and Other Safety Reporting: Definitions and Procedures for Recording, Evaluating, Follow-up, and Reporting**

### **10.4.1. Adverse Event Definitions and Classifications**

#### **Adverse Event**

An AE is any untoward medical occurrence in a clinical study participant administered a pharmaceutical (investigational or non-investigational) product. An AE does not necessarily have a causal relationship with the vaccine. An AE can therefore be any unfavorable and unintended sign (including an abnormal finding), symptom, or disease temporally associated with the use of a medicinal (investigational or non-investigational) product, whether or not related to that medicinal (investigational or non-investigational) product. (Definition per ICH).

This includes any occurrence that is new in onset or aggravated in severity or frequency from the baseline condition, or abnormal results of diagnostic procedures, including laboratory test abnormalities.

For the Safety Subset, any respiratory tract infection will be reported as an AE if it occurs between the time of any vaccination through the following 28 days. Any respiratory tract infection recorded as an AE in the eCRF will be excluded from the AE analysis if the molecular test is subsequently found to be positive for SARS-CoV-2. Respiratory tract infections arising from SARS-CoV-2 infection will not be reported as (S)AEs in the Clinical Study Report but will be tabulated separately.

As of Protocol Amendment 7, COVID-19 will be reported as SAE, AE, or MAAE.

*Note:* For time period of sponsor's AE collection, see All Adverse Events under Section [8.3.1](#).

#### **Serious Adverse Event**

An SAE based on ICH and EU Guidelines on Pharmacovigilance for Medicinal Products for Human Use is any untoward medical occurrence that at any dose:

- Results in death
- Is life-threatening  
(The participant was at risk of death at the time of the event. It does not refer to an event that hypothetically might have caused death if it were more severe)
- Requires inpatient hospitalization or prolongation of existing hospitalization
- Results in persistent or significant disability/incapacity
- Is a congenital anomaly/birth defect
- Is a suspected transmission of any infectious agent via a medicinal product

- Is Medically Important\*

\*Medical and scientific judgement should be exercised in deciding whether expedited reporting is also appropriate in other situations, such as important medical events that may not be immediately life-threatening or result in death or hospitalization but may jeopardize the participant or may require intervention to prevent 1 of the other outcomes listed in the definition above. These should usually be considered serious.

If a serious and unexpected AE occurs for which there is evidence suggesting a causal relationship between the study vaccine and the event (eg, death from anaphylaxis), the event must be reported as a SUSAR even if it is a component of the study endpoint (eg, all-cause mortality).

Any respiratory tract infection fulfilling the criteria of an SAE will be reported as such during the entire study. If the molecular test is positive for SARS-CoV-2, the SAE will be excluded from the SAE analysis in the Clinical Study Report, and will be tabulated separately.

As of Amendment 7, a passive follow-up approach is adopted: the investigator will place a phone call at Month 18 and Month 24 to collect information on any protocol required safety information (see Section 8.3.1). In addition, SAEs, AEs, and MAAEs related to COVID-19 need to be reported together with the concomitant medications related to these events until study end. Any confirmatory COVID-19 laboratory finding should be reported in the eCRF.

### **Unlisted (Unexpected) Adverse Event/Reference Safety Information**

An AE is considered unlisted if the nature or severity is not consistent with the applicable product reference safety information. For Ad26.COV2.S, the expectedness of an AE will be determined by whether or not it is listed in the IB.

#### **10.4.2. Attribution Definitions**

##### **Assessment of Causality**

The causal relationship to study vaccine is determined by the investigator. The following selection should be used to assess all AEs.

##### **Related**

There is a reasonable causal relationship between study vaccine administration and the AE.

##### **Not Related**

There is not a reasonable causal relationship between study vaccine administration and the AE.

The term “reasonable causal relationship” means there is evidence to support a causal relationship.

By definition, all solicited AEs at the injection site (local) will be considered related to the study vaccine administration.

### 10.4.3. Severity Criteria

All AEs and laboratory data will be coded for severity using a modified version of the FDA grading table, based on version of September 2007, included in [Appendix 9](#).

The AESI definition includes thrombocytopenia, defined as platelet count <150,000/ $\mu$ L as per the Brighton Collaboration (Section [8.3.7.1](#)).

For the purpose of severity grading, an AE of thrombocytopenia based on platelet counts >140,000/ $\mu$ L and <150,000  $\mu$ L should be considered Grade 1.

For AEs not identified in the grading table, the following guidelines will be applied:

Grade 1	Mild	Symptoms causing no or minimal interference with usual social and functional activities
Grade 2	Moderate	Symptoms causing greater than minimal interference with usual social and functional activities
Grade 3	Severe	Symptoms causing inability to perform usual social and functional activities and requires medical intervention
Grade 4	Potentially life-threatening	Symptoms causing inability to perform basic self-care functions OR medical or operative intervention indicated to prevent permanent impairment, persistent disability OR ER visit or hospitalization

For participants in the Safety Subset, the severity of solicited signs and symptoms will be graded in the e-Diary by the participant based on the severity assessment provided in the diary as well as assessed by the investigator using the toxicity grading scale in [Appendix 9](#). (Note: severity of the measured events will be derived from the diameter [for erythema and swelling] and the temperature measurements [for fever]). See also Section [8.3.2](#).

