### **8.3.7.1. Thrombosis with Thrombocytopenia Syndrome**

As described in Section 2.3.1, Risks Related to Study Participation, TTS has been observed very rarely following vaccination with Ad26.COV2.S and is considered an AESI in this study. TTS is a syndrome characterized by a combination of both a thrombotic event and thrombocytopenia.

Because this syndrome is rare and not completely understood, all cases of thrombosis and/or thrombocytopenia will be considered a suspected case of TTS until further adjudication can be performed. An AESI Adjudication Committee with appropriate expertise will be established to evaluate each suspected AESI and determine whether it is a case of TTS. The investigator shall be responsible for reporting any suspected AESI of TTS using the SAE form and the form detailed in Section 10.13, Appendix 13. A suspected TTS case is defined as:

Thrombotic events: suspected deep vessel venous or arterial thrombotic events as detailed in Section 10.14, Appendix 14

Thrombocytopenia, defined as platelet count below  $150,000/\mu\text{L}^9$  as per the Brighton Collaboration.

Symptoms, signs, or conditions suggestive of a thrombotic event should be recorded and reported as a suspected AESI even if the final or definitive diagnosis has not yet been determined, and alternative diagnoses have not yet been eliminated or shown to be less likely. Follow-up information and final diagnoses, if applicable, should be submitted to the sponsor as soon as they become available.

In the event of thrombocytopenia, study site personnel should report the absolute value for the platelet count and the reference range for the laboratory test used.

For either a thrombotic event or thrombocytopenia, testing for anti-PF4 should be performed at the local laboratory or substitute local laboratory; repeat testing may be requested for confirmation upon sponsor discretion.

Suspected AESIs will require enhanced data collection and evaluation (see Section 1.3.5). Every effort should be made to report as much information as possible about the AESI to the sponsor in a reasonable timeframe.

If an event meets the criteria for an SAE (Section 10.4.1), it should be reported using the same process as for other SAEs.

The form detailed in Section 10.13, Appendix 13 is intended as a guide for assessment of the AESIs to facilitate diagnosis and determine treatment options. If the investigator is not the treating

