### Protocol-Required Laboratory Assessments

As of Amendment 7, the number of on-site study visits will be reduced for participants who are not part of the Immunogenicity Subset and who are not part of the Booster Subset. In addition, no more laboratory samples will be collected in the context of a COVID-19 episode.

Text in italics below will no longer be applicable after implementation of Amendment 7.

Laboratory Assessments	Parameters	Timepoints
Testing done locally or substitute of a local laboratory	Urine pregnancy testing for participants of childbearing potential only	At screening and before each vaccination At additional timepoints as determined necessary by the investigator or required by local regulation
	Serum pregnancy testing for participants of childbearing potential only	At timepoints as determined necessary by the investigator or required by local regulation
	Nasal swabs for virology testing (molecular confirmation of SARS CoV 2 infection using a test approved by FDA EUA or equivalent)	On COVID 19 Day 1 2 (nasal swab collected by the participant at home) On COVID 19 Day 3 5 (nasal swab collected by qualified study staff) Once every 2 days following COVID 19 Day 3 5, until closure of the COVID 19 procedures (nasal sample collected by the participant at home)
	Serology blood sample for sero-confirmation of SARS-CoV-2 infection using a test approved by FDA-EUA or equivalent	At screening (prior to vaccination) (at the discretion of the sponsor)
	As of Amendment 7, any local COVID-19 confirmatory laboratory finding	At all visits after protocol amendment 7 (Month 12, 18, 24 or exit visit)
	Whole blood sample for platelet count which at some sites may be part of a complete blood count with differential	Pre-vaccination with Ad26.COV2.S: 
 
At Month 6/Unblinding Visit (if applicable)
 
At Year 1/Booster Visit, if applicable
 
 At the 28 days post Year 1/Booster Visit, if applicable As part of a suspected AESI investigation, if applicable

Laboratory Assessments	Parameters	Timepoints

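### Appendix 9 has no laboratory row, so thrombocytopenia at or below 140,000/µL has no count-based severity grade and falls to two functional scales that disagree

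*Protocol*

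**What the plan says.** Protocol Section 10.4.3 sets the grading instrument: "All AEs and laboratory data will be coded for severity using a modified version of the FDA grading table", based on the September 2007 version and said to be in Appendix 9 (Section 10.9). It adds one platelet rule: "For the purpose of severity grading, an AE of thrombocytopenia based on platelet counts >140,000" and below 150,000/µL is to be Grade 1.

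For anything outside the table it gives a fallback: "For AEs not identified in the grading table, the following guidelines will be applied". Grade 1 of the fallback reads "Symptoms causing no or minimal interference with usual social and functional activities". Grade 4 includes, besides inability to perform self-care, "OR medical or operative intervention indicated to prevent permanent impairment, persistent disability OR ER visit or hospitalization".

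Appendix 9 ends with its own general row for an illness or clinical adverse event. It is graded by interference with activity and need for medical intervention, with hospitalization as Grade 4.

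Section 8.3.7.1 sets the AESI threshold: "Thrombocytopenia, defined as platelet count below" 150,000/µL. It also says that "study site personnel should report the absolute value for the platelet count", together with the laboratory's reference range. Appendix 2 (Section 10.2) schedules a "Whole blood sample for platelet count which at some sites may be part of a complete blood count with differential" before cross-over vaccination, at the Year 1/Booster Visit before vaccination, 28 days after that visit, and in any AESI work-up.

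**The concern.** The instruction to grade laboratory data points to a table that grades none. The single platelet rule covers the shallowest band and is not attached to anything below it. Thrombocytopenia is one of the two components of TTS, the only named AESI. The scheduled draws can also find low counts in people who feel well. If the grade does not depend on the count, a deep fall and a borderline one can carry the same severity code. At stake are the severity coding of these events, any tabulation of graded laboratory data, and the identification of severe AEs. Section 9.7 names severe AEs as one of the grounds on which a narrative may be written.

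**Working it through.** No power, alpha or sample-size figure is involved. The check compares the texts and adds one proportion.

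**1. Contents of Appendix 9 (Section 10.9).**
- Local reactions: pain/tenderness, erythema, swelling.
- Vital signs: fever, tachycardia, bradycardia, systolic and diastolic hypertension, systolic hypotension, respiratory rate.
- Systemic (general): vomiting, nausea, diarrhea, headache, fatigue, myalgia.
- Systemic illness: the general row.

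There is no platelet row and no other laboratory row. The appendix runs straight into Appendix 10, with no redaction or missing-figure marker.

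**2. Share of the thrombocytopenia range with a count-based grade.**
- Range that defines thrombocytopenia: 0 to below 150,000/µL.
- Range with a count-based grade: above 140,000 to below 150,000/µL.
- Graded by count: 10,000 / 150,000 = 6.7% of the width.
- Not graded by count: 140,000 / 150,000 = 93.3%, including exactly 140,000/µL.

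These are shares of the numeric range, not of participants.

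**3. A symptom-free thrombocytopenia AE at or below 140,000/µL, traced through both scales.** Section 10.4.1 counts laboratory abnormalities as possible AEs, so such an AE can arise.

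| What happens | Section 10.4.3 fallback | Appendix 9 general row |
|---|---|---|
| No intervention, ER visit or hospitalization | Grade 1 | Grade 1 |
| ER visit only | Grade 4 | Grade 1 |
| Hospitalized | Grade 4 | Grade 4 |
| Intervention indicated to prevent permanent impairment or persistent disability | Grade 4 | Not clearly placed: Grade 3 also requires that daily activity is prevented |

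Neither column uses the count. In the first line, 30,000/µL is Grade 1, the same grade that the explicit rule gives to 148,000/µL.

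**4. Which scale applies.** The fallback is for AEs that the table does not identify. If the general row of Appendix 9 counts as identifying the event, the fallback is never reached; if it does not, the fallback governs. The protocol does not say which, and the ER-visit line shows that the answer can move a case from Grade 1 to Grade 4.

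**5. Laboratory values that are not AEs.** The fallback is worded for AEs only. A platelet result not recorded as an AE therefore has no scale below the explicit Grade 1 line, although Section 10.4.3 says that laboratory data are to be coded. The explicit line is itself worded for an AE of thrombocytopenia.

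**The case against.** A reader might infer that symptom-free severe thrombocytopenia is always coded Grade 1. The text does not support that. Fallback Grade 4 has routes that need no symptoms (a qualifying intervention, an ER visit, hospitalization), and hospitalization is also Grade 4 in the Appendix 9 row. The Grade 1 result holds only when none of these occurs. A reader might also infer that every low platelet count passes to the fallback; step 5 and the competing general row show otherwise.

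A third tempting inference is that deep falls would be hidden from the safety evaluation. They would not. Any count below 150,000/µL is a suspected AESI (Sections 8.3.1 and 8.3.7.1), reported within 24 hours whatever its seriousness or causality (Sections 8.3.7 and 10.4.5), and evaluated by an adjudication committee. Absolute counts are reported. Section 9.7 lists an AESI as a ground for a narrative separate from a severe AE. It lists or tabulates laboratory data as abnormal, or as graded where a grade is available, so abnormal values can appear ungraded. It describes frequencies by severity only for solicited AEs, and the safety analysis is descriptive.

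Exposure is also limited going forward. Under Amendment 7, booster vaccination stops apart from limited exceptions (Section 8.10), and outstanding Visits 8 and 9 are cancelled for participants outside the Immunogenicity and Booster Subsets (Section 8). Finally, the September 2007 table is not reproduced, so that the isolated Grade 1 rule was meant to extend a platelet row is an inference.

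All of this stands and narrows the harm. It does not remove the broken reference or the disagreement between the scales. Counts already collected still have to be graded for the remaining open-label and end-of-study analyses.

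**Conclusion.** The point holds as a defect in severity grading, not in case detection. Section 10.4.3 and Appendix 9 cannot both be followed for laboratory data. About 93% of the width of the thrombocytopenia range has no count-based grade. Within it, a symptom-free case with no qualifying intervention, ER visit or hospitalization is Grade 1 whatever the count, and an ER visit alone gives Grade 4 or Grade 1 depending on the scale used. The effect is limited to severity coding, graded laboratory tabulation and selection of severe AEs. The change should be made because it concerns a component of the only named AESI and costs little.

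The conclusion assumes that Appendix 9 is complete as shown and that the Grade 4 alternatives in Section 10.4.3 are separate routes. The number of participants affected cannot be derived, because the protocol gives no rate of low counts.

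**What to change.** Reconcile Section 10.4.3 with Appendix 9:

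- Add to Appendix 9 the platelet grading from the source table that Section 10.4.3 already cites, contiguous with the existing Grade 1 line and covering exactly 140,000/µL. The cut-offs must come from that source; none are proposed here.
- State that thrombocytopenia is graded by count, and not by the functional fallback or the general illness row.
- Derive the grades by program from the absolute counts that sites already report.
- Either delete the reference to laboratory data in Section 10.4.3 or add rows for every other laboratory value that is to be graded.

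The cost is one set of platelet entries, one sentence and a programmed derivation, with no new data collection. The downside is that some thrombocytopenia AEs will move to a higher grade.
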